- Quality of life/functional outcome comparisons using the KOOS Jr score, Oxford Knee Score (OKS), numerical rating scales (NRS) of gait/walking ability and sleep.
- Post-operative recovery comparisons using the Quality of Recovery 15 (QoR-15) survey and comparing average length of stay (LoS) for each study group

Questions to be answered:

- Is IORA of Diclofenac or systemic Diclofenac more effective in managing post-operative pain (as judged by VAS-P scores).
- 2. Will IORA of combined Diclofenac or systemic Diclofenac result in a more significant reduction in additional systemic opioid use for post-operative analgesia (as judged by MME).
- 3. Will IORA of Diclofenac or systemic Diclofenac provide better clinical improvement in knee health recovery and outcomes (as judged by KOOS Jr, OKS, NRS gait/walking ability and sleep, QoR-15, LoS).

Study Design

A prospective, double blinded RCT, with a single site cohort.

Patients and Methods

Patients who will be undergoing primary TKA for osteoarthritis will be eligible for this prospective study and randomised into two groups with 23 participants in each, one group receiving IORA Diclofenac (intervention group), and one group receiving IV Diclofenac (control group).

Power Calculation

There is a paucity of data evaluating the efficacy of IORA in pain management following TKA because it is a novel technique, although postoperative pain management is a thoroughly investigated area. Sample size was calculated based on previously published data investigating the efficacy of perioperative Celecoxib (a NSAID) on postoperative pain (VAS pain) after TKA [32]. This study showed statistically significant improvements in VAS pain scores for the intervention group (Celecoxib and PCA Morphine) at 48 hours and 72 hours after TKA, compared to the control group (PCA Morphine only). Mean VAS pain scores (in mm) in the intervention group were 21.3 ± 16.8 at 48 hours, and 17.8 ± 16.6 at 72 hours. Whereas VAS pain scores in the control group were 34.3 ± 15.0 at 48 hours, and 31.7 ± 20.1 at 72 hours.

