The minimal clinically important difference is defined as the smallest change in a measurement that signifies an important improvement in a symptom. MCID for VAS-P in acute pain management has a wide range, ranging from 8-40 mm, with a median of 17 mm [29]. In a review across 570 randomised controlled trials on postoperative pain management after total hip and knee arthroplasty, the median MCID for VAS-P was found to be 15 mm at rest and 18 mm during movement [30]. Another study demonstrated the mean MCID for VAS postoperative pain improvement in TKA patients to be 22.6 mm [33]. There is yet to be a standardised value for postoperative VAS-P MCID, but based on recent literature and consensus we have chosen an MCID of 20 mm to suggest clinically relevant improvements in pain relief between the intervention and control groups [34].

Using this data, a priori power analysis was calculated using this data, which found that 22 patients in each arm would provide >95% statistical power to detect the expected difference in pain relief (MCID of 20 mm) at the 5% significance level between IORA Diclofenac and systemic (IV) Diclofenac. An additional patient in each group (5%) will bring each group to 23 patients to account for loss of follow up.

Inclusion Criteria

Informed consent obtained - both written and verbal

Patient undergoing primary total knee arthroplasty for Osteoarthritis

Age \geq 18 and \leq 80 years old (inclusive)

Exclusion Criteria

Patient lacking capacity to consent to the research project

BMI ≥ 40

Pregnancy or suspected pregnancy

Pain Catastrophising Scale score ≥ 30 points

Previous infection of knee joint

Rheumatoid/inflammatory arthritis

Undergoing bilateral total knee replacement, revision total knee arthroplasty, or any additional procedure outside of a primary total knee arthroplasty

Precluded from having general anaesthesia

Patients with lower limbs not amenable to effective tourniquet use

Contraindications to Diclofenac:

[figure not shown]
- Established allergy or hypersensitivity to Aspirin or other NSAID including attacks of asthma, angioedema, urticaria, or acute rhinitis
- Severe renal disease (GFR<30 mL/min/1.73m²)
- Severe cardiac failure
- Hepatic failure
- Active gastric or intestinal ulcer, bleeding or perforation
- Recent myocardial infarction (within last 12 months)
- History of asthma
- History of haemorrhagic diathesis

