A patient reported outcome questionnaire to measure the quality of recovery after anaesthesia, which is important in determining early postoperative health status of patients.

Outcomes

Preoperative Outcome Measurements

The following outcome measurements will need to be completed by patients prior to their surgery. Baseline scores will be averaged for each study group:

- PCS A PCS score of ≥ 30 represents clinically relevant catastrophising and will exclude patients from the study.
- PDI
- KOOS, Jr
- OKS
- Preoperative VAS-P score
- Preoperative opioid use (MME) Participants will be required to report any and all opioid
 pain medications (including Tramadol and Codeine) they use as well as the average daily
 amount of opioid medications in milligrams that they take. For example, 20 mg of Sevredol
 daily. This will be converted into a preoperative baseline MME.

Postoperative Outcome Measurements

The primary outcome of this study will be patient pain levels during the early stages of recovery following primary total knee arthroplasty. To monitor this, pain at rest scores will be recorded by the patient using the Visual Analogue Scale (VAS; 0-100 mm from "no pain" to "worst pain possible"). The distance between "no pain" and the patient-made mark is to be measured to the nearest 1 mm.

Post-operatively, once the patient has arrived at the recovery unit, pain scores are to be recorded at the following time points: 1 hour, 2 hours, 3 hours, 4 hours, 5 hours, 12 hours, and 24 hours post-op. These numbers will be recorded by a recovery nurse who will be blinded to the treatment group, and by a treating physio the following day. Patients will also record twice daily VAS-P scores at 8am and 5pm from post-op day 1, up to post-op day 7, into a pain diary supplied to them. These twice daily recordings will be used to calculate daily averages of pain scores. All VAS-P scores are to be recorded for 'pain at rest'.

The minimal clinically important difference (MCID) of 20 mm for VAS-P scores will be used to determine the clinical significance of pain relief in the intervention group compared to the control group.

Secondary outcomes which focus on function, pain, satisfaction, and health related quality of life:

• Total Morphine Milligram Equivalent (MME) of additional postoperative opioid medications required for 1 week post-op (from post-op day 0 to post-op day 7).

- Quality of recovery after anaesthesia (as per QoR-15 survey), recorded post-op day 1.

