Means, standard deviation, and 95% confidence intervals will be calculated for the participant VAS-P scores at each recorded time interval as the primary objective of the study. A general linear model or generalised linear mixed model, followed by independent two-sample t-test or Wilcoxon non-parametric rank sum test will be used to analyse the data. VAS-P scores will be pooled according to the appropriate study group for comparison between the study arms. An MCID of 20 mm will be used to determine a clinically significant difference in pain management (but not necessarily statistical significance).

For secondary objectives, independent two-sample t-test or Wilcoxon non-parametric rank sum test will be used to compare means of MME, LoS, QoR-15, satisfaction, gait, sleep, OKS, KOOS Jr scores between the intervention group and control group.

The intended statistical test used will be dependent on the distribution of the data collected. This will be determined by appropriate normality and homogeneity testing of the data. If requirements

are not met, a transformation may be applied, which will likely be logarithmic. Adjustments will be made accordingly based on the data obtained.

Baseline characteristics and preoperative survey scores will be compared using a two sample t-test or Wilcoxon non-parametric rank sum test. Gender comparisons between the two study groups will need to be analysed using a two-way analysis of variance (ANOVA) or in the case of non-parametric testing, Kruskal-Wallis test.

Adverse events will be recorded separately and reviewed by investigators for relevance to the procedure/intervention as well as commonalities. Frequency and percent distributions will be presented in tabular form and logistic regression will be used for comparison of the study groups.

The statistical principles of this protocol have been reviewed by a Consultant Statistician who will also oversee statistical analysis.

Selection Criteria for Investigators/Sites

- The investigator(s) participating in this study is(are) qualified Orthopaedic surgeon(s).
- Research assistants and study staff will be under the direction of the Principal investigator.
- Conflicts of interest (including financial assistance from other parties) will be declared by Investigators and research personnel before starting the trial.
- A list entailing any persons, their qualifications, and their roles relating to the trial, must be kept by the investigators.

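### The primary test and its scale are chosen from the outcome data, and the named log fallback is undefined at VAS 0 and not on the 20 mm scale used for sample size and clinical relevance

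*Protocol*

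**What the plan says.** All of the analysis text is in the protocol section Data Capture and Analysis. It first plans VAS-P means, standard deviations and 95% confidence intervals at each recorded time. It then lists a general linear model or generalised linear mixed model, followed by a t-test or a Wilcoxon rank-sum test. Of the choice among these it says "The intended statistical test used will be dependent on the distribution of the data collected", to be settled by unnamed normality and homogeneity tests. If the requirements "are not met, a transformation may be applied, which will likely be logarithmic", and further adjustment according to the data is allowed.

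The same section states "An MCID of 20 mm will be used to determine a clinically significant difference in pain management", and adds that this is separate from statistical significance.

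Under Postoperative Outcome Measurements, VAS-P is a 0–100 mm scale read to the nearest 1 mm, so a mark at the no-pain end is recorded as 0. Under Power Calculation, which works at a 5% level, the sample size rests on the same 20 mm: "22 patients in each arm would provide >95% statistical power to detect the expected difference in pain relief (MCID of 20 mm".

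**The concern.** Three things do not fit together.

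- **Choice after the data.** The primary test and scale are settled by looking at the outcome data. The wording is permissive throughout, so two analysts could follow it and report different primary results.
- **A fallback that fails on this outcome.** The log of 0 does not exist, and 0 is a legitimate pain-at-rest score. The same holds for additional-opioid MME and the 0–10 rating items, to which the section's test-choice rule also appears to apply.
- **Scale.** The trial is sized for a difference in means of 20 mm and judges relevance at 20 mm. A log analysis yields a ratio and a rank-sum test yields a p-value about ranks. The test could then answer a different question from the one the trial was sized for.

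At stake is whether the primary p-value and the estimate set against 20 mm describe the same quantity, fixed in advance.

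**Working it through.** **1. The plan's own sample size.** Power Calculation gives 72-hour SDs of 16.6 and 20.1 and 48-hour SDs of 16.8 and 15.0. It names no single SD, and I assume a two-sided 5% test.

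- Pooled SD at 72 h: √((16.6² + 20.1²)/2) = 18.43. At 48 h: √((16.8² + 15.0²)/2) = 15.93.
- n per arm = 2(1.960 + 1.645)² SD²/20². This gives 22.1, so 23, at 72 h and 16.5, so 17, at 48 h. With the t distribution it is 24 and 18.
- Power at 22 per arm (t distribution): 94.0% with the 72-hour SD and 98.3% with the 48-hour SD. An SD of 17.97 gives exactly 95%.

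The stated figure is reproduced to within rounding. It is a calculation for a difference in means on the untransformed mm scale.

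**2. How likely is a zero?** The protocol gives only means and SDs, so the shape is an assumption. Take the 72-hour intervention figure (17.8, SD 16.6) and a beta distribution on 0–100 with that mean and SD.

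- k = 0.178 × 0.822/0.166² − 1 = 4.31, so a = 0.178k = 0.77 and b = 0.822k = 3.54.
- P(rounds to 0) = P(X < 0.5 mm) = 4.8%. At least one zero in 22: 1 − (1 − 0.0476)²² = 66%.
- Control arm at 72 h (31.7, SD 20.1): 0.26% per reading and 5.6% per arm. Either arm: 1 − 0.342 × 0.944 = 68%; simulation gave 69%.
- At 48 h (21.3, SD 16.8): 1.6% per reading and 29% of arms.
- A crude normal curve at 72 h: Φ((0.5 − 17.8)/16.6) = 15% per reading and 97% of arms.

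**3. How often would the fallback be triggered?** Shapiro–Wilk at 5% in each arm, 22 per arm, one reading per patient:

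| Assumed shape | Normality rejected in at least one arm | Trial contains a zero |
|---|---|---|
| Beta, 72-hour figures | 86% | 69% |
| Normal(14, 21.5) floored at 0 (27% zeros), no difference | 96% | 100% |
| Same floored model, true difference about 11 mm | 83% | 100% |

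For patient means of 14 readings in the floored model with no difference, rejection falls to 34%, 54% and 76% at assumed within-patient correlations of 0.3, 0.5 and 0.7.

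**4. Does the choice change the answer?** The t-test and the log(x+1) t-test disagree on significance in 12–13% of trials under the beta model with the 72-hour means (31.7 − 17.8 = 13.9 mm). Under the floored model the figure is 16% at about 11 mm, and about 8% at 20 mm.

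**5. Scale.** A ratio of 0.60 is a difference of 0.40 × control mean: 12.7 mm at 31.7, 20 mm at 50 and 24 mm at 60. No fixed ratio equals 20 mm.

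**6. Type I error with no true difference.**

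| Rule | Beta model | Floored model |
|---|---|---|
| t-test alone | 4.7% | 5.1% |
| Shapiro–Wilk, then t or rank-sum | 4.8% | 5.4% |
| Smallest p of t, rank-sum, log(x+1) | 7.4% | 7.6% |

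**The case against.** The strongest reply is that the 20 mm rule can still be applied. The section plans VAS-P means with confidence intervals in mm at every time point whichever test is used, and separates the 20 mm rule from significance. A rank-sum analysis can also carry a Hodges–Lehmann shift in mm; with a true 20 mm difference it averaged 20.1 mm in simulation. This stands. A reader might infer that no mm difference would exist to set against 20 mm, and the document does not support that. What remains is that the between-arm difference in mm, with its interval, is not fixed as the primary estimate and need not match the test.

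Second, a reader might infer that pre-testing inflates false positives. It does not when followed strictly (step 6). The 7.4–7.6% arises only if the smallest of three p-values is picked. The loose wording permits this but does not prescribe it.

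Third, the high trigger and zero rates use the arm and time with the lowest mean relative to its SD, and a single reading. The Objectives speak of means over one week, for which both the skew and the chance of an exact 0 are smaller. This also stands, and the rates are quoted with that limit.

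Fourth, the offset for zeros, back-transformation and the named normality test are ordinary SAP matters. Agreed, and their absence is not the point. The protocol states a data-driven rule and names a fallback; an SAP that fixed one mm-scale test would have to depart from that text.

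A reader might also infer that the general linear model option would treat repeated readings as independent. The text does not say so, and no conclusion is drawn from it.

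**Conclusion.** The point holds in this form. The protocol lets tests on the outcome data choose the primary test and scale, and its named fallback cannot be computed at a valid score of 0. The significance test may therefore be on a ratio or rank scale while the sample size and relevance rule are on the mm scale.

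The size depends on the assumed distribution. With the 72-hour figures and a single reading, the fallback would be the usual route (about 86% of trials) and zeros would be common (about 69%). Both fall for averaged scores, and zeros are also rarer at 48 hours. The choice of test would change the significance call in roughly one trial in six to eight at true differences of 11–14 mm, and less often at 20 mm. Type I error stays near 5% under strict pre-testing, with about 7.6% as a worst case. This should be corrected before analysis; it does not invalidate the design.

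**What to change.** For VAS-P, delete the sentences that make the test depend on the observed distribution and that offer a log transform. Name one primary analysis on the raw mm scale that accounts for repeated readings within a patient; the mixed model already listed would serve. State that it reports the between-arm difference in mean VAS-P in mm with its 95% CI, and set that estimate against 20 mm. Keep rank-sum or transformed analyses as labelled sensitivity analyses. For secondary outcomes that can be 0 (MME and the 0–10 ratings), do not leave a plain log as the stated fallback.

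The cost is a few sentences. It needs no new data, and 22 per arm (23 with the loss allowance) is unchanged, because that calculation is already for a mean difference in mm.

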Multiple surgeons who regularly perform TKA will carry out this procedure on all patients included in the trial. Prior to all surgeries, each patient will undergo a general anaesthetic (GA) for their procedure, and no patients will have a neuraxial and/or peripheral nerve block. This will involve total IV anaesthesia with IV Propofol and IV fentanyl, as well as Ketamine and/or Clonidine in small amounts as adjuncts to the GA. The airway will be maintained via laryngeal mask airway. As part of usual TKA protocol 2g IV Cephazolin, 2g IV Tranexamic acid, and 16mg IV Dexamethasone will also be administered. The Patient will then be positioned appropriately for surgery and a single cuff tourniquet applied to the upper thigh of the marked limb. Following standard patient preparation

and draping of the appropriate limb, the limb is exsanguinated, and the tourniquet inflated to cease blood flow in the limb at 250-300 mmHg for the duration of the procedure (60-90 minutes). A proximal tibial IO cannula will then be inserted, and the study medication administered into bone immediately before skin incision [6, 7].

There will be two groups into which patients will be randomised; 23 patients will be randomised into each group:

- Group 1: IORA 75mg Diclofenac preoperatively (intervention group).
- Group 2: IV infusion 75 mg Diclofenac preoperatively (control group).

For the patients randomised to the IORA Diclofenac group, following tourniquet inflation a proximal tibial cannula will be inserted. The study medication will be administered via the cannula into bone immediately before skin incision. 75mg Diclofenac (75 mg/3 mL ampoules) will be made up to 10mL with normal saline 0.9% in a syringe to dilute the medication prior to administration. The medication will then be injected as a bolus by the blinded surgeon. Immediately after, 500 mg of Vancomycin in 110 mL normal saline 0.9% will be delivered intraosseously. These patients will also receive a preoperative IV infusion of 100 mL normal saline 0.9% over 2 minutes by the blinded anaesthetist. The infusion will finish at least 3 minutes prior to tourniquet inflation.

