A record of the patient's date of birth, age, gender, weight, height, BMI, and medical history will be obtained pre-operatively at time of consent.

Patient Catastrophising Scale (PCS)

A self-reported measure which assesses catastrophic thinking in the context of actual or anticipated pain. Pain catastrophising is associated with poor pain treatment response in patients with chronic pain [35].

Pain Disability Index (PDI)

A widely used tool for determining pain-related disability. It measures the degree to which chronic pain disrupts different aspects of life.

KOOS, Jr Survey

The Knee Injury and Osteoarthritis Outcomes Score for Joint Replacement survey provides a single score that represents "knee health" as it combines pain, symptoms, and functional limitations [31]. It is a patient reported outcome measurement instrument developed to assess the patient's opinion about their knee and associated problems.

Oxford Knee Score (OKS)

A patient-completed 12-item questionnaire, designed specifically for patients undergoing total knee replacement. Relates to an individual's level of function, activities of daily living, and how they have been affected by pain. Each of the 12 items has 5 scoring categories. It is short, practical, reliable, valid and sensitive to clinically important changes over time.

Visual Analogue Scale Pain (VAS-P)

A graphic VAS will be used as a measurement instrument for patients to indicate their level of pain on a scale from 'No Pain' to 'Worst Pain Possible'. VAS is a continuous spectrum to represent pain.

Morphine Milligram Equivalent (MME)

MME is the amount of morphine in milligrams equivalent to the strength of the opioid dose prescribed. This measurement will allow for a standardised comparison of opioid use between study groups.

Patient Satisfaction

Numerical rating scale (NRS; 0-10) for grading a patient's satisfaction with their knee replacement, from 'completely dissatisfied' to 'completely satisfied'.

Gait/Walking Ability and Sleep

NRS (0-10) for grading how pain has interfered with a patient's walking ability and sleep over the past 24 hours, from 'does not interfere' to 'completely interferes'.

Average Length of Stay (LoS)

Each patient's length of stay in hospital will be recorded from day of admission to day of discharge.

Quality of Recovery (QoR-15)

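### The protocol fixes a two-way ANOVA, with Kruskal-Wallis as its non-parametric alternative, for comparing gender between the arms; the pairing is wrong whichever comparison was meant

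*Protocol*

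**What the plan says.** The Protocol, Data Capture and Analysis, has a short paragraph on comparing the arms before surgery. It opens: "Baseline characteristics and preoperative survey scores will be compared using a two sample t-test or Wilcoxon non-parametric rank sum test". The next sentence deals with gender: "Gender comparisons between the two study groups will need to be analysed using a two-way analysis of variance (ANOVA". The fallback that this sentence then gives reads: "or in the case of non-parametric testing, Kruskal-Wallis test".

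Gender appears elsewhere as a demographic item. Under Patient Demographics, "age, gender, weight, height, BMI, and medical history will be obtained pre-operatively". It is not named as an outcome or in an objective. There are two arms, and "23 patients will be randomised into each group".

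Methods suited to categorical data do appear in the same section, but only for adverse events: "Frequency and percent distributions will be presented in tabular form and logistic regression will be used for comparison of the study groups". No test of proportions is named for gender anywhere in the protocol.

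**The concern.** The sentence does not leave the method open. It prescribes one, and that method does not match the data it would be applied to. A two-way ANOVA needs a continuous response and two factors. A comparison of gender between two arms has a binary response and one factor. The fallback is also not a counterpart of the first choice, because Kruskal-Wallis handles one grouping factor only.

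What is at stake is limited. An analyst following the text cannot set up the named analysis for the baseline table. An analyst who takes it as an outcome analysis has no stated outcome, and has a fallback whose result cannot be attributed to treatment, gender or their interaction. An analyst who does the sensible thing departs from the written protocol, which under Modification of Protocol may not be changed without Ethics Committee approval.

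**Working it through.** The protocol gives no figure to reproduce here, so the check takes each reading of the sentence in turn.

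**Inputs**
- From the protocol: two arms of 23, N = 46; gender recorded as a baseline item; the two tests named.
- Assumed, because the protocol gives no gender counts: 8/23 v 16/23 women as an illustration.
- Assumed for the simulation: mean pain 30 mm in one gender and 45 mm in the other, so a 15 mm gender effect; SD 17 mm; 11 patients per arm-by-gender cell; no treatment effect; no interaction. The SD lies within the 15.0 to 20.1 mm quoted in Power Calculation. The cell size gives 2 x 11 = 22 per arm, the number in the power statement.

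**Reading 1: baseline comparison of gender between arms**

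The data form a 2x2 table of arm by gender. Arm is the only factor and gender is the response. There is no second factor, so a two-way ANOVA cannot be specified.

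Kruskal-Wallis can be computed. With ties corrected, on a binary variable in two groups, it is H = [(N - 1)/N] x Pearson chi-square.

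For 8/23 v 16/23:
- Chi-square = N(ad - bc)² / (product of the margins) = 46 x (8 x 7 - 15 x 16)² / (23 x 23 x 24 x 22) = 46 x 33,856 / 279,312 = 5.576, p = 0.018.
- H = (45/46) x 5.576 = 5.455, p = 0.0195.

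Kruskal-Wallis is thus an odd name for what is nearly a chi-square test. The outright mismatch on this reading is the two-way ANOVA.

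**Reading 2: an outcome compared by arm and gender**

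A two-way ANOVA is now defined, but the sentence names no outcome. The fallback can be run in two ways, and neither replaces the ANOVA:
- On the two arms only, it ignores gender.
- On the four arm-by-gender cells, it tests whether any cell differs from any other, so a gender difference alone will trigger it.

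The second was simulated with 4,000 data sets under the assumptions above, where gender is the only effect:

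| Test | Rejections at 5% |
|---|---|
| Kruskal-Wallis over four cells | 59.6% |
| Two-way interaction test | 4.7% |

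The Monte Carlo standard errors are √(0.596 x 0.404/4,000) = 0.8 percentage points and √(0.047 x 0.953/4,000) = 0.3 points. The interaction test holds its level. The four-cell Kruskal-Wallis test rejects often although treatment does nothing.

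**The case against.** The strongest defence has three parts.

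First, the words two-way may signal that arm and gender are both factors for a continuous outcome. A two-way ANOVA would then be suitable, and the objection about a binary response would fall. That is possible, although the placement among baseline comparisons points the other way. It does not rescue the sentence, because the Kruskal-Wallis fallback remains wrong and the outcome is unstated.

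Second, a reader might infer that the planned tests would give misleading p-values. For assumed counts of 8/23 v 15/23, a one-way F-test gives p = 0.040 and Kruskal-Wallis p = 0.041, while Fisher's exact test gives p = 0.076. This inference fails. The uncorrected Pearson chi-square gives p = 0.039 for the same table. By exact enumeration with 23 per arm and a true share of 0.4 to 0.6, the F-test, Kruskal-Wallis and chi-square all have a size of 5.1 to 5.4%, against about 2.5% for Fisher's test. The contrast reflects the conservatism of Fisher's test, not an error in the other tests. The F-test in this example is also one-way, which is not what the protocol names.

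Third, a reader might infer that a small baseline p-value would lead to ad hoc covariate adjustment, or might object to baseline significance tests in general. The protocol has no rule linking a baseline p-value to adjustment. Its remark that adjustments will follow from the data closes the paragraph on normality and transformation, before baseline comparisons are mentioned. Testing baseline variables is uninformative in a randomised trial but common. It does not bias the treatment comparison, and it is a separate matter of preference.

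The planned oversight by a consultant statistician limits the practical risk, but it does not correct the text.

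**Conclusion.** The sentence is wrong as written, at minor severity. On the baseline reading, which its position favours, a two-way ANOVA does not apply to a 2x2 table. On the outcome reading, no outcome is named and Kruskal-Wallis cannot stand in for a two-way ANOVA. No other part of the protocol corrects it.

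The first conclusion rests on no assumed number. The figure of about 60% on the second reading depends on the assumed 15 mm gender effect, SD and cell size, and would move with them; with no gender effect it would fall to about the nominal level. The structural point, that a one-way test cannot separate arm, gender and interaction, does not depend on it.

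The documents do not support saying that trial conclusions would be distorted. The primary VAS-P analysis and the sample size do not use this sentence.

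**What to change.** In Data Capture and Analysis, delete the ANOVA and Kruskal-Wallis wording for gender. State instead that gender will be reported as counts and percentages by arm, with a chi-square or Fisher's exact test only if a p-value is wanted.

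If the intention was to examine whether the treatment effect differs by gender, say so separately: name the outcome, add an arm-by-gender term to the model for that outcome, and label the analysis exploratory.

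The cost is one sentence, or two if the exploratory analysis is wanted, plus the Ethics Committee approval that any protocol modification requires. No data collection, sample size or primary analysis changes.
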